4.2 General Concomitant Medication and Supportive Care Guidelines

Patients may receive Epogen/Procrit/Aranesp for anemia as required. Anti-emetic therapy of any kind is permitted. Full transfusional support is permitted. The prophylactic use of growth factors is not allowed. The use of pyridoxine (vitamin B6) for the treatment of hand-foot syndrome is permitted.

No other approved or investigational anticancer treatment will be permitted during the study period, including chemotherapy, biological response modifiers, hormone therapy or immunotherapy. No other investigational drug may be used during treatment on this protocol, and concurrent participation in another clinical trial is not allowed.

Axitinib is metabolized primarily by liver enzymes, in particular CYP3A4. Agents known to induce CYP3A4 including dexamethasone should be avoided. Agents known to inhibit this enzyme (e.g., grapefruit juice) should also be avoided. In particular, ketoconazole should be avoided if possible, since a clinical interaction study of axitinib indicated that up to a 2-fold increase in plasma levels of axitinib was induced by ketoconazole. In addition, concomitant treatment with the following drugs with dysrhythmic potential (i.e., terfenadine, quinidine, procainamide, disopyramide, sotalol, probucol, bepridil, haloperidol, risperidone, and indapamide) is not recommended.

4.3 Duration of Therapy

Treatment may continue until one of the following criteria applies:

- A total of 8-10 weeks of axitinib therapy (at which point partial/radical nephrectomy would be undertaken at the discretion of the operating surgeon). A decision regarding nephrectomy will be made at re-staging done at week 8 of therapy.
- Disease progression, as defined by RECIST criteria, v1.1,
- Intercurrent illness that prevents further administration of treatment,
- Unacceptable adverse event(s)
- Patient decides to withdraw from the study, or
- General or specific changes in the patient's condition render the patient unacceptable for

further treatment in the judgment of the investigator.

- If axitinib treatment is unsuccessful (i.e. is unable to render a large and complex mass for a partial nephrectomy), radical nephrectomy would be offered. The large size of the masses will mean that they are of significant risk oncologically to the patient and as such would not be candidates for an alternative approach such as radiofrequency or cryoablation (utilized when tumors are less than <3.5 cm in size) or active surveillance.

5. STUDY CALENDAR

	≤ 4 weeks prior to dosing	Baseline	Day 14 (± 3 days)		Day 28 (± 3 days)	End of Cycle (Day 58 ± 3 days)	End of Treatment ¹
Informed Consent	X						
Vital Signs/ECOG	X	X	X		X	X	X
History / Physical	X	X	X		X	X	X
Hematology ²	X	X*	X		X	X	X
Chemistries ³	X	X*	X		X	X	X
Coagulation ⁴	X					X	
Pregnancy Test ⁵	X						
Urinalysis ⁶	X				X	X	X
Drug Related AE's		X	X		X	X	X
TSH, T3, T4	X					As clinically indicated	X
Axitinib**		X-----X					
Tumor Imaging ⁷	X				X	X	

* Cycle 1, day 1 labs need not be repeated if done within 14 days. ;** Nephrectomy will be performed ≥ 1 days after the last dose of Axitinib

Footnotes for Schedule of Events

1. End of Treatment/Withdrawal: These assessments will occur at least 30 days after nephrectomy date.
2. Hematology: CBC with differential, platelets
3. Blood Chemistry: Albumin, total bilirubin, bicarbonate, BUN, calcium, chloride, creatinine, glucose, magnesium, phosphorus, potassium, SGOT [AST], SGPT [ALT], sodium, ALP, LDH (baseline only).
4. Coagulation: PT/INR and PTT
5. Pregnancy Test: Serum or urine test must be performed for all women of childbearing potential.
6. Urinalysis: with 24 hour urine to ensure protein < 2 grams for anyone with 2+ or greater protein on urinalysis.
7. Tumor Imaging: CT or MRI scan of the chest, abdomen and pelvis (with IV contrast, if possible) to be performed to assess disease status at screening, prior to nephrectomy and whenever disease progression is suspected. CT or MRI scan of the chest is optional at day 28 based on symptoms or pre-enrollment findings. CNS and bone imaging needed only if clinical signs/symptoms are suggestive. Follow up imaging after nephrectomy at the discretion of the treating MD and not part of this protocol.

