In the full analysis set, median overall survival (OS) was 20.1 months versus 19.2 months for axitinib versus sorafenib, respectively (HR: 0.969; 95% CI: 0.800–1.174; p 5.3744; cutoff of November 1, 2011). There was no survival benefit of axitinib over sorafenib in the prior sunitinib treatment group (HR: 0.997; 95% CI: 0.782–1.270), but a positive trend for OS was observed for axitinib over sorafenib in the prior cytokine treatment group (HR: 0.813; 95% CI: 0.555–1.191), with median OS of 29.4 months in the axitinib arm and 27.8 months in the sorafenib arm.

The analysis of objective response rate (ORR) showed a statistically significant improvement of 13.9% for axitinib compared with sorafenib in patients pretreated with cytokines. In the prior sunitinib treatment group, the difference in ORR between axitinib and sorafenib was 3.6%. The groups of patients previously treated with temsirolimus and bevacizumab plus IFN α were very small (n 524 and n 559, respectively); therefore, no firm conclusions could be made regarding the efficacy in these subgroups. There were no differences between treatment groups in terms of patient-reported outcomes (Functional Assessment of Cancer Therapy-Kidney Symptom Index; EuroQol Group's Self-Reported Health Status Measure) in the overall population.²¹

Clinical Safety

A total of 3,655 subjects (phase I–III studies) were evaluated for safety, including 2,507 (68.6%) who received at least one dose of axitinib. Updated data from 3,944 subjects treated in 42 clinical trials were also provided.

The most common adverse events reported in the axitinib group (in \geq 20% subjects) were diarrhea, hypertension, fatigue, dysphonia, nausea, decreased appetite, and palmar plantar erythrodysesthesia (hand-foot) syndrome. Most of these events occurred with grade 1 or 2 severities.

The most important serious adverse reactions reported in patients receiving axitinib were thromboembolic events, hemorrhage, gastrointestinal perforation and fistula formation, hypertensive crisis, and posterior reversible encephalopathy syndrome. In total, 36 deaths occurred in the axitinib arm versus 25 in the sorafenib arm. The majority of these events were due to progressive disease. Five events in each arm were considered treatment related. There is no indication that axitinib promotes disease progression or the development of new lesions.

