Axitinib affected the incidence of hypertension and thyroid dysfunction, and sometimes aggravated these conditions if they were pre-existing. The hypertension reported during the study was largely manageable, but hypertension is still considered an unfavorable effect of axitinib.

There did not seem to be any clear signal of a clinically meaningful prolongation of the QT interval observed with axitinib; however, two patients had grade 3 QTc prolongation at cycle 1, day 15, and two additional patients had on treatment increase in QTc .60 ms in the pivotal study. Consequently, to get the most optimal information about new suspected cases, applicant Pfizer included enhanced pharmacovigilance activities with use of a questionnaire to systematically collect follow-up data of individual case safety reports that can be associated with QT prolongation.²²

A risk management plan was submitted to address additional important potential risks (wound healing complications; congestive heart failure and cardiomyopathy; carcinogenicity; and drug interactions with CYP1A2, 2C8, and P-glycoprotein substrates) and important missing information (safety in pregnant and lactating women, in pediatric patients, in relevant malignancies, in patients with moderate and severe renal impairment, and in patients with severe hepatic impairment).

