4.1 Axitinib Administration

Pfizer will supply Axitinib and it will be shipped in labeled boxes, with unlabeled bottles inside. The pharmacy must have labeling capabilities and fax all requests to Pfizer using the Drug Supply Request Form. Contact information is as follows:

[name], CCRC
[contact]
[contact]
[contact]

Pfizer will be provided with detailed mailing instructions, address/location of Pharmacy, Pharmacist in charge, or anything else that may be helpful for shipping.

Treatment will be administered on an outpatient basis. Axitinib will be initially dosed at 5 mg po BID with or without food. Patients tolerating axitinib at week 4 with no more than grade 2 toxicity and blood pressure controlled to $< 140/90$ mmHg (medication permitted) will have axitinib dose increased to 7mg BID. Axitinib will be dosed for a total of 8-10 weeks.

Swallow axitinib whole with a glass of water; do not split, crush, or chew. If the patient vomits

or misses a dose, an additional dose should not be taken; the next prescribed dose should be taken at the usual time

No investigational or commercial agents or therapies other than axitinib may be administered with the intent to treat the patient's malignancy.

Axitinib should be held for 1 day prior to surgery.

No axitinib will be administered after nephrectomy for any patient.

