6. DOSING DELAYS AND MODIFICATIONS

Patients will be monitored closely for toxicity, and the axitinib dose may be adjusted according to individual patient tolerance.

Table 2: Suggested Dose Modification Algorithms for Potential Treatment-Related Adverse Events

AE Terms & Descriptions	Dose Modification Algorithms
Hypertension	
(A). Hypertension: If persistent hypertension occurs despite antihypertensive medications, reduce dose; discontinue if hypertension is severe and persists despite dose reduction	Step 1. Continue investigational product (IP) at the current dose. Step 2. Adjust current or initiate new antihypertensive medication(s). Step 3. Titrate antihypertensive medication(s) during next 2 weeks as indicated to achieve well-controlled ^a blood pressure (BP). If BP is not well-controlled within 2 weeks, consider referral to a specialist and go to scenario (B).
(B). Hypertensive crisis:	Discontinue Axitinib
(C). Hemorrhage	If any bleeding requires medical intervention, temporarily interrupt axitinib dose.
(D). Reversible posterior leukoencephalopathy syndrome:	Discontinue axitinib
(E) Moderate-to-severe proteinuria	Reduce dose or temporarily interrupt treatment
(F) Strong CYP3A 4/5 inhibitors:	Avoid coadministration if possible, if axitinib must be coadministered, decrease dose by ~50% and then adjust according to safety and tolerance; if strong CYP3A4/5 inhibitor is discontinued, may increase to prior axitinib dose after waiting 3-5 half-lives of the inhibitor
(G) Renal Impairment	Based on population pharmacokinetic analyses, no significant difference in clearance observed in patients with pre-existing mild-to-severe renal impairment
(H) Hepatic Impairment	Mild (Child-Pugh A): No adjustment of initial dose is required Moderate (Child-Pugh B): Decrease initial dose by ~50%; subsequent doses can be increased or decreased based on individual safety and tolerability Severe (Child-Pugh C): Has not been studied

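### After the week-4 increase to 7 mg BID, no blood pressure or drug-related AE check is scheduled from Day 28 to Day 58; add one at Day 42

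*Protocol*

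**What the plan says.** Section 4.1 starts axitinib at 5 mg BID. At week 4, patients with no more than grade 2 toxicity and blood pressure below 140/90 mmHg go up a dose level, and antihypertensives may be used to meet the limit: "medication permitted) will have axitinib dose increased to 7mg BID". Total dosing is 8 to 10 weeks.

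The Section 5 calendar marks vital signs and drug-related adverse events at Baseline, Day 14, Day 28, the column reading "End of Cycle (Day 58 ± 3 days", and End of Treatment. Of that last column, footnote 1 says: "These assessments will occur at least 30 days after nephrectomy date". The calendar's one unlabelled column lies between Day 14 and Day 28 and carries no marks.

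Section 6 opens with a general commitment: "Patients will be monitored closely for toxicity, and the axitinib dose may be adjusted according to individual patient tolerance". Its Table 2 is titled "Suggested Dose Modification Algorithms for Potential Treatment-Related Adverse Events". For hypertension it advises adjusting antihypertensives and titrating them over two weeks. If hypertension persists despite medication, the instruction is "reduce dose; discontinue if hypertension is severe and persists despite dose reduction".

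On expected toxicity, Section 2.4.2 says of the common adverse events: "Most of these events occurred with grade 1 or 2 severities". On blood pressure it says: "The hypertension reported during the study was largely manageable, but hypertension is still considered an unfavorable effect of axitinib".

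**The concern.** The protocol treats blood pressure as the toxicity that limits dosing. It makes escalation conditional on it, and it excludes patients who already need two or more antihypertensives because little could be added if axitinib raised their pressure. Yet scheduled checks become sparser at the point where the dose goes up. Day 58 is the first scheduled reading after the increase and the only one before surgery.

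Hypertension can be symptomless, so without a reading it may go unfound. The patients enrolled have chronic kidney disease, a solitary kidney or bilateral tumours. Section 2.4.2 lists hypertensive crisis among the important serious reactions to axitinib, and names safety in moderate and severe renal impairment as missing information. At stake is patient safety during the first month at the higher dose. No endpoint, power figure or estimate depends on it.

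**Working it through.** The protocol gives no figure of its own to reproduce here. The check is a reading of the calendar plus the lengths of the intervals.

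**Inputs**

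- Dose 5 mg BID, then 7 mg BID from week 4 (Section 4.1).
- Visits at Day 14, Day 28 and Day 58, each ± 3 days (Section 5). The windows are Day 11 to 17, Day 25 to 31 and Day 55 to 61.
- Treatment for 8 to 10 weeks, i.e. to Day 56 or Day 70 (8 × 7 and 10 × 7).
- Planned n = 50 (Schema).
- Assumptions: the dose is raised at the Day 28 visit, and an added Day 42 check has the same ± 3-day window (Day 39 to 45).

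**Dose step.** 2 × 5 = 10 mg per day becomes 2 × 7 = 14 mg per day; 14/10 − 1 = 40%.

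**Intervals between scheduled checks, in days.** Nominal = later day − earlier day. Shortest = start of the later window − end of the earlier one. Longest = end of the later window − start of the earlier one.

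| Interval | Nominal | Shortest | Longest |
|---|---|---|---|
| Day 14 to 28 (5 mg BID) | 28 − 14 = 14 | 25 − 17 = 8 | 31 − 11 = 20 |
| Day 28 to 58 (7 mg BID) | 58 − 28 = 30 | 55 − 31 = 24 | 61 − 25 = 36 |
| With the addition: Day 28 to 42 | 42 − 28 = 14 | 39 − 31 = 8 | 45 − 25 = 20 |
| With the addition: Day 42 to 58 | 58 − 42 = 16 | 55 − 45 = 10 | 61 − 39 = 22 |

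The interval after the increase is 30/14 = 2.1 times the one before it. It equals 30/56 = 54% of the length of an 8-week course, or 30/70 = 43% of a 10-week course.

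**Fit with the protocol's own algorithm.** Table 2 allows two weeks for antihypertensive titration. Hypertension first found at Day 58 would complete that step at 58 + 14 = Day 72, after the latest planned end of dosing (Day 70). In a patient who stops at 8 weeks (Day 56), the nominal Day 58 visit falls after the last dose, so the whole period at 7 mg BID could pass without a scheduled on-drug reading. Hypertension found at Day 42 would complete titration at 42 + 14 = Day 56, and the existing Day 58 visit could confirm control before surgery.

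**Other provisions that might fill the gap**

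- The close-monitoring sentence in Section 6 names no interval and no reading.
- Table 2 manages hypertension once it is known, and schedules nothing that would detect it.
- The week-4 blood pressure condition and the antihypertensive exclusion both act before the increase.
- The monthly committee in Sections 7 and 11 reviews reported safety data and does not examine patients.

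**The case against.** The strongest reply is that nothing here is wrong or contradictory. The protocol promises no two-weekly checks, and visit frequency is a matter of judgement. Escalated patients have been selected for tolerance: four weeks on drug, toxicity no worse than grade 2 and controlled pressure, with uncontrolled hypertension and heart failure excluded at entry. Denser visits at first exposure and sparser ones later in proven tolerators is a coherent design, and no passage says the two periods need equal spacing. Section 6 does commit to close monitoring. A patient who met the week-4 condition on newly changed antihypertensives would be rechecked under Table 2 at about Day 42 anyway. Section 2.4.2 is fairly reassuring on severity. In the 24-patient neoadjuvant axitinib study described in Section 2.4.3, one patient stopped early for adverse events, although only a 5 mg dose is reported there.

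Part of this stands. The harm is unquantified, and the patients left uncovered are mainly those whose hypertension is new and symptomless after the increase. Patients kept at 5 mg BID share the 30-day gap, and those treated to week 10 have no scheduled on-drug check after Day 58; a Day 42 check limited to escalated patients closes neither gap. The fall from 36 to 22 days applies only to the Day 28 to Day 58 window.

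What does not stand is that existing provisions fill the gap. Tolerance at 10 mg per day does not show tolerance at 14 mg. Calling hypertension manageable presupposes that it has been found. The shared gap does not weaken the case for the patients given 40% more drug.

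**Conclusion.** The concern holds. No vital signs or drug-related adverse-event assessment is scheduled between Day 28 and Day 58, a gap of 30 days (24 to 36) at the higher dose against 14 days (8 to 20) at the lower. This assumes that the dose is raised at the Day 28 visit; a later increase would shorten the time at 7 mg BID before the next check. Sites may well measure blood pressure informally, but the protocol does not require it at any stated time. Because no rate of hypertension after 7 mg BID is given, the benefit cannot be put in numbers. The change is worth making as an inexpensive safety measure; the statistical validity of the trial does not depend on it.

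**What to change.** Add to the Section 5 calendar a Day 42 (± 3 days) blood pressure and drug-related adverse-event check for patients raised to 7 mg BID at Day 28. A brief visit, or a home blood pressure reading with a telephone contact, is enough.

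The cost is a calendar amendment and one short contact per escalated patient, so at most 50 contacts even if every enrolled patient escalates. No imaging, laboratory test or procedure is added.

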2.4.3 Clinical Efficacy in Neoadjuvant Setting

Karam et al. performed a single-institution, single-arm phase 2 clinical trial. Patients with locally advanced nonmetastatic biopsy-proven ccRCC were eligible. Patients received axitinib 5mg for up to 12 wk. Axitinib was continued until 36h prior to surgery. Patients underwent partial or radical nephrectomy after axitinib therapy.

The primary outcome was objective response rate prior to surgery. Secondary outcomes included safety, tolerability, and quality of life. A dedicated radiologist independently reviewed all computed tomography scans to evaluate for response using Response Evaluation Criteria in Solid Tumors (RECIST).

A total of 24 patients were treated. Twenty-two patients continued axitinib for 12 wk; 1 patient continued axitinib for 11 wk and underwent surgery as planned. One patient stopped treatment at 7 wk due to adverse events (AEs). Median reduction of primary renal tumor diameter was 28.3%. Eleven patients experienced a partial response per RECIST; 13 had stable disease. There was no progression of disease while on axitinib. The most common AEs were hypertension, fatigue, oral mucositis, hypothyroidism, and hand-foot syndrome. Postoperatively, 2 grade 3 and 13 grade 2 complications were noted. No grade 4 or 5 complications occurred. Functional Assessment of Cancer Therapy-Kidney Specific Index-15 changed over time, with quality of life worsening while on therapy, but by week 19, it was not statistically different from screening. Limitations include single-arm design and small patient numbers. The authors concluded that axitinib was clinically active and reasonably well tolerated in the neoadjuvant setting in patients with locally advanced nonmetastatic ccRCC, though larger studies are needed prior to further clinical use.¹⁹

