- 9) Other severe acute or chronic medical or psychiatric condition or laboratory abnormality that may increase the risk associated with study participation or study drug administration, or may interfere with the interpretation of study results, and in the judgment of the investigator would make the subject inappropriate for entry into this study.
- 10) Uncontrolled HTN
- 11) HTN with need for 2 or more anti-hypertensives to control it at baseline (because there isn't room to add more antihypertensives if axitinib causes increased BP)
- 12) CHF since axitinib can cause CHF
- 13) Baseline abnormal thyroid function tests
- 14) subjects with arterial thrombotic events in the prior 12 months (axitinib has never been studied in this population)
- 15) subjects who have had venous thrombotic events in the prior 6 months (axitinib has never been studied in this population)

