Results from drug-drug interaction studies conducted in subjects with cancer suggest that there will be no clinically relevant pharmacokinetic interaction between axitinib and hypoglycemic agents. Transient decreases in serum glucose (mainly Grade 1 and 2, rarely Grade 3) have been observed in clinical studies with pazopanib. In addition, decreases in blood sugar have been recently reported in subjects treated with sunitinib. Such changes may require an adjustment in the dose of hypoglycemic and/or insulin therapy. Subjects should be advised to report symptoms of hypoglycemia (e.g., confusion, visual disturbances, palpitations, sweating). Serum glucose should be tested during treatment with pazopanib as outlined in the protocol and as clinically indicated.

The Effects of Axitinib on Other Drugs^{1,2}

Axitinib is metabolized primarily in the liver by cytochrome P450 (CYP) 3A4/5 and, to a lesser extent (<10 % each), by CYP1A2, CYP2C19, and uridine diphosphate glucuronosyltransferase (UGT) 1A1. The two major human plasma metabolites, M12 (sulfoxide product) and M7 (glucuronide product), are considered pharmacologically inactive. Axitinib is eliminated via hepatobiliary excretion with negligible urinary excretion. Although mild hepatic impairment does not affect axitinib plasma exposures compared with subjects with normal hepatic function, there was a 2-fold increase in AUC from time zero to infinity (AUC_{∞}) following a single 5-mg dose in subjects with moderate hepatic impairment. In the presence of ketoconazole, a strong CYP3A4/5 inhibitor, axitinib C max and AUC_{∞} increased by 1.5- and 2-fold, respectively, whereas co-administration of rifampin, a strong CYP3A4/5 inducer, resulted in a 71 and 79 % decrease in the C max and AUC_{∞} , respectively. Axitinib does not inhibit CYP3A4/5, CYP1A2, CYP2C8, CYP2A6, CYP2C9, CYP2C19, CYP2D6, CYP2E1, or UGT1A1 at concentrations obtained with the clinical doses and is not expected to have major interactions with drugs that are metabolized by these enzymes.

In addition, the potential for drug interaction with such medications, although diminished, may persist after the last dose of axitinib even with its relatively short half-life (i.e., 2.5-6.1 hours); therefore, continue to exercise **CAUTION** for at least 1 day and up to 2 days after the last dose of axitinib when administering these medications. These medications include

(but are not limited to):

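### No thyroid sample is required while patients are on axitinib, so thyroid changes that are silent and short-lived can be missed and detection depends on discretionary testing

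*Protocol*

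**What the plan says.** In the calendar of Protocol section 5, the TSH, T3, T4 row has a fixed entry within the 4 weeks before dosing and another at End of Treatment. The only entry between them reads "As clinically indicated". Days 14 and 28 are blank in the row as extracted. If the wording spans more columns in the source table, the tests are still not mandatory on drug.

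Three statements fix how far the last sample lies from dosing:

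- Footnote 1, on End of Treatment or withdrawal: "These assessments will occur at least 30 days after nephrectomy date".
- The note under the calendar: "Nephrectomy will be performed ≥ 1 days after the last dose of Axitinib".
- Section 4.1: "No axitinib will be administered after nephrectomy for any patient".

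On the thyroid effect itself, section 2.4.2 says "Axitinib affected the incidence of hypertension and thyroid dysfunction". Section 2.4.3, describing the neoadjuvant axitinib trial, says "The most common AEs were hypertension, fatigue, oral mucositis, hypothyroidism, and hand-foot syndrome". Neither gives a rate. The exclusion criteria in section 4 include "Baseline abnormal thyroid function tests". Section 1 names safety among the secondary objectives.

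**The concern.** Patients enter with normal thyroid tests, so an abnormal value during the 8 to 10 weeks of dosing would be new and fairly easy to interpret. That is the period in which the calendar requires no test. The one compulsory follow-up sample comes after drug withdrawal and a major operation, when a reversible change may have resolved and a persisting one is harder to attribute.

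Testing on indication finds patients whose signs or symptoms prompt it and leaves silent cases unseen. In a multicenter study it also makes the recorded frequency depend partly on how readily investigators order the test. At stake is the completeness of one part of the adverse-event profile. The primary endpoint is not affected.

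**Working it through.** The Protocol states no figure on this point, so there is none to reproduce. The check counts scheduled samples, dates the last one, and asks what the schedule can detect.

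**1. Scheduled samples on drug.** Hematology and chemistry are mandatory at Days 14, 28 and 58, and coagulation at Day 58. Mandatory thyroid panels at these visits: 0.

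**2. Timing of the fixed follow-up sample.**
- Last dose to nephrectomy: at least 1 day. Nephrectomy to End of Treatment: at least 30 days.
- Minimum time off drug: 1 + 30 = 31 days, or 31 × 24 = 744 hours.
- Dosing lasts 8 to 10 weeks (section 4.1), so the last dose falls at about Day 56 to Day 70. The earliest End of Treatment sample is then about Day 56 + 31 = 87 to Day 70 + 31 = 101.

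**3. What drug clearance shows.** Appendix 1 gives a half-life of 2.5 to 6.1 hours. The interval is 744 / 6.1 = 122 to 744 / 2.5 = 298 half-lives, so essentially no drug remains. This says nothing about how long a thyroid abnormality lasts once the drug is gone, and the Protocol gives no recovery time. The half-life count therefore does not measure the loss of cases.

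**4. What the schedule captures.** Among patients with an on-drug abnormality, let c be the share detected by discretionary testing on drug. Let s be the share of the remainder still abnormal at End of Treatment. Then

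share captured = c + (1 − c) × s.

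Neither c nor s is in the Protocol. The values below are assumptions for illustration:

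| c | s | Share captured |
|---|---|---|
| 0.25 | 0.25 | 0.25 + 0.75 × 0.25 = 44% |
| 0.50 | 0.50 | 0.50 + 0.50 × 0.50 = 75% |
| 0.75 | 0.75 | 0.75 + 0.25 × 0.75 = 94% |

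Capture is complete only if c = 1 or s = 1. Otherwise some on-drug cases are lost, but the range is too wide to support a single figure.

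**5. Safety window.** Section 7 follows toxicity until 30 days after partial nephrectomy, longer only where there is drug-related toxicity. The End of Treatment sample is due at 30 days or later. A first abnormal thyroid result may therefore arrive after routine follow-up has closed.

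**The case against.** The strongest reply is that symptom-triggered testing is a deliberate choice and contradicts nothing else in the Protocol. Adverse events, history and examination, and vital signs are recorded at Days 14, 28 and 58, and safety is reviewed monthly. The safety indices named in section 1 are surgical complications and multiple transfusions. Section 10 plans no thyroid analysis, and the stopping rule in section 11 does not depend on one. All of this stands. It limits the point to completeness of adverse-event recording, but it does not supply an on-drug value for a patient without symptoms.

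A reader might infer three stronger things that the Protocol does not support:

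- **That thyroid dysfunction will certainly be under-counted because axitinib has been cleared.** Clearance is not thyroid recovery. An abnormality that outlasts surgery would be found by the End of Treatment sample.
- **That hypothyroidism is common by the Protocol's account as a whole.** That description comes from one trial of 24 patients, with no rate. The list in section 2.4.2 of events in at least 20% of axitinib subjects omits it.
- **That patients face added operative risk from unrecognised hypothyroidism.** The Protocol contains nothing on this, and the point does not rest on it.

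**Conclusion.** The point holds as a gap in ascertainment. No thyroid sample is required on axitinib, and the only fixed one after screening is at least 31 days off drug. On-drug changes that are both symptom-free and resolved by End of Treatment can be missed, and what is found in between depends on discretionary testing.

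The size of any loss cannot be stated. The 44% to 94% capture shares follow wholly from assumed inputs. The conclusion rests on the calendar as printed and on the Protocol's own statement that axitinib affects thyroid function. It does not rest on the half-life. No named endpoint or decision rule is at risk. This is a worthwhile, low-cost improvement in safety data and does not threaten the trial's main result. It cannot be left to an analysis plan, because samples never drawn cannot be recovered.

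**What to change.** In the section 5 calendar, change the TSH, T3, T4 entry at End of Cycle (Day 58 ±3) to a fixed X, to be drawn before nephrectomy with the hematology, chemistry and coagulation samples already scheduled there. Record the date of the last dose with it: 8 weeks of dosing ends at about Day 56 and the visit window runs from Day 55 to Day 61, so some samples may fall just after the last dose.

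Keep the End of Treatment sample for all patients. Making it conditional on an abnormal Day 58 result would save assays, but dosing can run to about Day 70. A sample at the start of the window could precede the last dose by 70 − 55 = 15 days, and dysfunction arising after it would never be tested. The later sample also shows persistence.

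Report thyroid abnormalities at End of Cycle and after surgery separately, and keep tests done on indication distinguishable from scheduled ones.

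Cost: a calendar amendment and at most about 50 added panels (one per patient at the planned 50), with no extra visit or blood draw. The reported frequency of thyroid events may rise because more are looked for.
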